9.1.2.2. Secondary endpoints

The following secondary endpoints will separately investigate each type of event globally appraised by the primary endpoint:

- Time to CVE occurrence and CVE distribution in time according to classification MACE and non-MACE (See section 9.3.10)
- Time to Adverse Drug Reaction (ADR)
- Time to Serious Adverse Drug Reaction (SADR)
- Beck Depression Inventory global score at each collection time

9.1.2.3. Exploratory endpoints

Effectiveness

Change from patient inclusion date to the end of study as evaluated with:

- Epworth Sleepiness Scale (ESS) global score
- Maintenance of wakefulness test (MWT) mean sleep latency
- Multiple Sleep Latency Test (MSLT) mean sleep latency
- Fatigue Severity Scale (FSS) global score

Adherence

- Rate of patients compliant with their OZAWADE® treatment (according to the 8-item Morisky Score) at each visit
- Rate of patients compliant with their primary therapy (according to the mean number of hours of use per night during the last three months) at each visit.

Other

Incidence of car accidents at driving (comparison of answers to the questionnaire "assessment of sleeping at driving" between inclusion and yearly evaluation)

9.1.3. Patient discontinuation and study termination

The patients are free to withdraw from the study at any time without prejudice to their drug prescriptions or therapeutic management. In this case, their data will be collected up to the time of withdrawal, with no additional information collected thereafter. The patients have also the right to oppose to the use of their personal data for the purpose of the study without prejudice to future medical care by the participating physician. However, in this case and in the case of withdrawal, any adverse events (AE) will still be

collected/reported and followed-up until resolved or stabilised or until the patient died or is lost to follow-up.

Missing evaluations at one or several time points is not a criterion for patient withdrawal.

A patient may be withdrawn from the study prior to completion in case of patient consent withdrawal and physician's or Sponsor's decision and/or safety reason. If the patient withdraws or is withdrawn, the reason will be collected in the eCRF.

All patients discontinuing OZAWADE® will be maintained in the study until completion of the follow-up period.

The participating physicians may interrupt their participation to the study at any time and will immediately inform Bioprojet Pharma.

Bioprojet Pharma reserves the right, at any time, to discontinue enrolment of additional patients into the study, at any site; or to discontinue the study, for medical or administrative reasons and will inform all study stakeholders.

9.2. Setting

9.2.1. Physician Selection and Initiation

9.2.1.1. Type of Physician

Physician selection will aim to recruit physicians specialized in sleep medicine who receive, in medical consultation, OSA patients with diagnosis of EDS and who are likely to treat them with OZAWADE (sleep specialists, pulmonologists, cardiologists, otorhinolaryngologists and neurologists).

9.2.1.2. Sampling

A feasibility study is on-going to identify physicians that could be interested in participating in the study, to evaluate the patient potential and the clinical routine care of OSA patients in the four countries where the study will take place. For the purpose of this feasibility study, the Sponsor established a pre-identified list of about 15 centers experienced in sleep disorders and distributed throughout each country. The study will then be proposed to all physicians that declared to have an interest in participating in the study.

A recruitment mail containing the study summary, the site qualification questionnaire and a reply coupon will be sent to all identified physicians.

9.2.1.3. Site Initiation

Participating physicians will receive a study kit once all the necessary administrative procedures have been completed (confidentiality agreement, financial agreement, CV, etc., where applicable).

The study kit includes at least the following:

- The study protocol;
- The physician identification form;
- The patient information note and non-opposition note or the patient information note and Informed Consent Form where applicable;
- The medical records release forms;
- Blood pressure monitors;
- Patient diaries;
- The patient Contact Order Form;
- The sample baseline and follow-up Case Report Forms (CRFs) and questionnaires; The eCRF manual user;

- The patient log;
- Pre-paid envelopes.

Upon receipt of the study kit, an initiation telephone call will be organized by the CRO in charge of the project to explain the protocol, data collection, and the practical aspects of the study.

9.2.2. Patient Selection, Enrolment and Follow-up

9.2.2.1. Selection Criteria

Inclusion Criteria

A patient must meet all of the following criteria to be eligible for participation in the study:

- 1. Patients with OSA, treated or not by primary therapy (e.g., CPAP, MAD).
- 2. Patients eligible for treatment by OZAWADE® as per SmPC (being prescribed or not with OZAWADE®).
- 3. Patients naive of treatment with any wake-promoting agent or patients previously treated with wake-promoting agent for less than six months and having discontinued the treatment for at least three months.
- 4. Patient informed about the study and who either did not oppose to their data collection or who signed the Informed Consent Form when applicable.

Reminder: OZAWADE® shall be prescribed according to the SmPC and treatment guidelines to patients diagnosed with OSA. The decision to prescribe OZAWADE® will necessarily precede and will be independent of the decision to enrol the patient into the study.

Exclusion Criteria

A patient who meets the following criterion is not eligible for participation in the study:

- 1. Patient participating in a clinical trial.
- 2. Patient under curatorship or deprived of liberty.

Reminder: contraindications to OZAWADE® as identified in the SmPC are:

- Hypersensitivity to the active substance or to any of the excipients of OZAWADE®;
- Severe hepatic impairment (Child-Pugh C);
- Breastfeeding.

9.2.2.2. Patient Enrolment

During the enrolment period, participating physicians will be asked to report in a patient log all eligible patients presenting for consultation. This log will therefore list all eligible patients whether they accept to participate in the study or not. The overall representativeness of the patients enrolled in the study population will be assessed from the data collected in this patient log.

During the 2-year enrolment phase, 502 patients are planned to be recruited in four to five countries where OZAWADE® is available on the market (i.e., France, Germany, Italy and possibly Netherlands, Belgium or Spain), in approximately 8 to 15 centers per country. In each center, participating physicians will enrol all eligible patients consecutively according to a systematic sampling technique (i.e., in chronological order of their arrival at the consultation) irrespective of the treatment decision (i.e. patients prescribed and not prescribed OZAWADE®) until the recruitment target is reached globally in both groups or until the end of the enrolment period.

During the recruitment phase, and for each patient, participating physicians will:

- Explain the study to the patient, in particular, the objective of the study and its observational nature. Indications will be given on the aim and timelines for visits, as per routine clinical practice.
- Give the patient, either the "patient information and non-opposition note" or the "patient information note and Informed Consent Form", where locally applicable, and ask the patient to read it. After sufficient time to consider his/her decision, the patient will confirm (or not) his/her oral agreement (for non-opposition) to participate (which will be also recorded in the patient medical records) or sign (or not) the Informed Consent Form (when locally applicable).
- For patients who agree to participate in the study: give the baseline patient reported outcome (PRO) questionnaires and ask the patient to complete the questionnaires.

9.2.2.3. Planned follow-up

The data will be collected during the normal course of patient care at approximately 6, 12, 24, 36, 48 and 60 months. During the follow-up visits, participating physicians will complete the eCRF with the data required to properly answer to the study objectives.

9.3. Variables

The data collected will be those data that the investigating centers are used to assess during routine visits, exception made of some Clinician- or Patient- Reported Outcomes (ClinROs, PROs) questionnaires (see below) planned to properly answer to the study objectives. The following assessments have no obligation to be performed and only the available measures and assessments will be collected in the CRF.

9.3.1. Site Selection Questionnaire

To assess potential selection bias of the participating physicians, the following data will be collected from all physicians contacted during the selection process.

- Country;
- Specialty;
- Age;
- Department;
- Institution type/patient flow.

9.3.2. Demographic and Baseline Characteristics

The following patient's demographic and baseline characteristics will be collected:

- Only at study inclusion:
 - Age (MONYYYY);
 - Gender (Male/Female);
 - Height;
 - Socio-professional status;
 - Date of OSA diagnosis (MONYYY);
 - Relevant medical history including (but not limited to) the following past cardiovascular risk factors:
 - Arterial hypertension, defined according to international guidelines, or the current use of antihypertensive drugs (international non-proprietary name);
 - Atrial fibrillation;
 - Diabetes mellitus (Type 1 or Type 2);
 - Hypercholesterolemia (HDL and LL cholesterol) (6.42 mmol/l in peripheral blood or current use of treatment);
 - Stroke, or transient ischemic attack;

- Ischemic heart disease with or without myocardial infarction;
- Carotid stenosis (more than 50% Doppler).
- At study inclusion and at each follow-up visits:
 - o Weight;
 - Waist circumference;
 - Smoking status:
 - Never smoker;
 - Former smoker. If yes, number of pack-year and the year when they stopped smoking:
 - Current smoker. If yes, number of pack-year.
 - Current daily alcohol consumption (in glass: 1 glass = 10 g alcohol);
 - Physical activity (sport duration per week [hours]);
 - O Duration of sleep (hours) as reported by the patients;
 - Perceived sleepiness at driving (assessment of 4 questions) (will not be done at the 6month follow-up visit).

9.3.3. Electrocardiogram (ECG)

Patients with cardiac disease, hypertension, at risk of major adverse cardiovascular events (MACE), comedicated with other QT-prolonging medicinal products or known to increase the risk of repolarization disorders, or co-medicated with medicinal products that significantly increase pitolisant Cmax and AUC ratio or patients with severe renal or moderate hepatic impairment should be carefully monitored.

ECG data are required to analyse the QT interval (Fridericia's QTc interval) when available. ECG data will be centrally read and interpreted in order to detect prolonged QT interval. ECG data will be collected both at study inclusion and at each follow-up visit.

9.3.4. Blood pressure and heart rate

Blood pressure and heart rate will be collected both at study inclusion and at each follow-up visit, and it will be measured as follows:

- One assessment during each follow-up site visit;
- Self-assessment during the month following each visit: patients will use blood pressure monitors and will report the data in a patient diary.

9.3.5. Beck Depression Inventory (BDI)

The BDI is a validated self-administrated questionnaire to measure the severity of depression. It is composed of 13 multiple-choice questions (with four possible answer choices, ranging in intensity) about how the patient has been feeling in the last week. Each question is rated on a 4-point scale (0-3). The total BDI score is obtained by summing the score of the 13 items (0-39). The total score is compared to a key to determine the depression's severity (0-3: No depression; 4-7: mild depression; 8-15: moderate depression; 16-39: severe depression). BDI data will be collected both at study inclusion and at each follow-up visit (except for the 6-month follow-up visit).

9.3.6. Disease activity

OSA and EDS will be evaluated according to routine clinical practice by the tool and ClinROs/PROs questionnaires described below:

• Apnoea-hypopneoa index (AHI)

The AHI is a diagnostic tool for determining the presence and severity of OSA. AHI is measured with CPAP device or by polysomnography. It is calculated by dividing the total number of apnoeic and hypoapnoeic events by the total number of hours of sleep by night. The data can be systematically collected from CPAP software in those under CPAP during each follow-up visits. AHI data will be collected both at study inclusion and at each follow-up visit.

• Epworth Sleepiness Scale (ESS)

The ESS is a short validated self-administered questionnaire (PRO) to measure a subject's usual level of daytime sleepiness or average sleep propensity [14, 34]. It is composed of 8 questions, each describing a different daily life situation. Each question is rated on a 4-point scale (0-3) and total ESS score is obtained by summing the scores of the eight items (0-24). The higher the ESS score, the higher that person's average sleep propensity in daily life or their daytime sleepiness. ESS data will be collected both at study inclusion and at each follow-up visit.

Maintenance of wakefulness test (MWT) or Multiple Sleep Latency Test (MSLT)

The MWT is a validated polysomnographic test for the evaluation of daytime sleepiness/wakefulness [35]. It evaluates a subject's ability to remain awake while resisting the pressure to fall asleep during soporific circumstances.

MSLT evaluates the tendency to fall asleep under controlled conditions [36]. The test consists of four to five naps given two hours apart during the day, following a standardized procedure. Both tests allow the measure of the mean sleep latency as the measure of sleepiness.

MWT and MSLT data will be collected both at study inclusion and at each follow-up visit (except for the 6-month follow-up visit).

• Fatigue Severity scale (FSS)

The FSS is a validated self-report scale of nine items which measures the severity of fatigue and its effect on a patient's activities and lifestyle. Answers are scored on a seven point scale (1-7). The total FSS score is obtained by summing the score of the nine items (9-63). The higher the score, the more severe the fatigue and the more it affects the person's activities. FSS data will be collected both at study inclusion and at each follow-up visit (except for the 6-month follow-up visit).

9.3.7. Exposure and adherence to OZAWADE®

9.3.7.1. Treatment exposure

Exposure to OZAWADE® will be collected at inclusion and at follow-up visits (if not started at inclusion), with the date of prescription and the prescribed dose.

At each follow-up visit, dose modifications, treatment interruptions and permanent discontinuation will be collected. Reasons of changes will also be collected.

9.3.7.2. Adherence

Adherence to OZAWADE® will be assessed at each follow-up visit using the Morisky Medication Adherence Scale 8-item (MMAS-8) questionnaire. A paper questionnaire will be provided by the participating physician during the follow-up visits and will be self-administered by the patient in the waiting room.

The MMAS-8 questionnaire is a validated 8-item self-report measure of medication-taking behaviour [37]. Each of the eight items measures a specific medication-taking behaviour and not a determinant of adherence behaviour. Response categories are yes/no for each item with a dichotomous response and a 5-point Likert response for the last item. Total MMAS-8 scores can range from 0 to 8 and have been categorized into three

levels of adherence: high adherence (score = 8), medium adherence (score of 6 to < 8), and low adherence (score < 6). MMAS-8 data will be collected only at each follow-up visit.

9.3.8. Prior and concomitant medications or therapies

OSA primary therapy

The use of CPAP of alternative therapy (e.g., MAD) will be collected both at study inclusion and at each follow-up visits. The following data will be collected:

- Start date (MONYYYY);
- o Mean number of hours of use per night during the last three months;
- Discontinuation (Yes/No). If yes: date and primary reason of discontinuation.
- Prior and concomitant medications

Prior (last three months before inclusion) and concomitant medications will be recorded as text fields. The data on prior medication will be collected only at study inclusion. The data on concomitant medications will be collected both at study inclusion and at each follow-up visits. For concomitant medications, the dosage regimen, the route of administration, and the dates of use will also be collected.

9.3.9. Laboratory assessments

Biological assessments of less than 12 months (cholesterol, glycemia and triglyceridemia) will be collected at study inclusion and at each follow-up visit (except for the 6-month follow-up visit).

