9.1. Study design

9.1.1. Overall Design of the Study

This is a prospective, observational, multi-center, open-label, long term, cohort study (OZAWADE® exposed and OZAWADE® unexposed) designed to collect data on the long-term safety of OZAWADE® treatment. This study will be conducted in OSA patients with EDS whose EDS has not been satisfactorily treated by, or who have not tolerated OSA primary therapy. The study will be conducted by physicians specialized in sleep management such as sleep specialists, pulmonologists, cardiologists, otorhinolaryngologist and neurologists.

[figure not shown]
As an observational study, the assignment of the patient to a particular therapeutic strategy should be decided within the current clinical practice and the decision to prescribe OZAWADE® should necessarily precede and be independent of the decision to enrol the patient into the study. OZAWADE® should be prescribed and used based on the routine clinical practice as well as on the individual situation of each patient, according to the approved SmPC.

During the 2-year enrolment phase, 502 patients are planned to be recruited in four to five countries where OZAWADE® is on the market (*i.e.*, France, Germany, Italy and possibly Netherlands, Belgium or Spain), in approximately 8 to 15 centers per country.

Once eligible patients are enrolled, baseline data should be collected. Data collected in the CRF will correspond to data collected in routine practice in the investigating centers.

Patients will be followed-up up to five years, during which time they should be assessed by their treating participating physicians at 6, 12, 24, 36, 48 and 60 months, to follow routine care schedule.

Study visits, procedure and evaluations are summarized in the study flow (Figure 1) and schedule of assessments below (Table 2).

CPAP: Continuous Positive Airway Pressure; EDS: Excessive Daytime Sleepiness; FU: Follow-up; MAD: Mandibular Advancement Device; OSA: Obstructive Sleep Apnoea.

Figure 1: Study Flow.

PASS Protocol [P21-02/OZAWADE]

OZAWADE

Table 2. Schedule of Assessments

	Procedures ¹ /Visits	Inclusion	FU 6 Months	FU Year 1	FU Year 2	FU Year 3	FU Year 4	FU Year 5	End of study
	Visit window		6M [3-9M[12M [9-18M[24M [18-30M[36M [30-42M[48M [42-54M[60M [54-66M[
	Demography: age, gender	X	ē.						
	Profession / Socio-economic status	Х							
Patient interview	Height², weight	Х	Х	Х	X	X	X	X	Х
nten	Waist circumference	X	х	Х	X	X	X	х	Х

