anti	Smoking status ³	X ₃	X ³	X ³	X ₃	X ₃	X ₃	X ₃	X ³
Patie	Alcohol consumption	X	х	Х	X	X	X	X	х
	Physical activity	Х	Х	X	X	X	X	X	Х
	Relevant medical history	X							
	Prior medications (last three months)	X							
	Relevant concomitant medications	X	Х	Х	X	X	X	X	Х
e e	Physical examination	X		Х	X	X	Х	X	х
minati	All Adverse Events including adverse events of special interest ⁴		х	х	х	х	X	x	х
l exa	Blood pressure, heart rate	X	Х	Х	X	X	X	X	X
Medical examination	Biological assessment of less than 12 months (cholesterol, glycemia and triglycedemia)	х		х	х	х	х	х	Х
	ECG brought by the patient when available (QT measure) ⁵	X _e	X ⁶	X ⁶	X _e	Xe	Xe	X _e	X _e

PASS protocol Version 3.0 – 23 NOV 2023

PASS Protocol [P21-02/OZAWADE]

OZAWADE

	Procedures /Visits Visit window		FU 6 Months	FU Year 1	FU Year 2	FU Year 3	FU Year 4	FU Year 5	End of study
			6M [3-9M[12M [9-18M[24M [18-30M[36M [30-42m[48M [42-54[60M [54-66[
OSA and sleep history	OSA and sleep history, duration of sleep	X	X ⁷	Х	х	X	Х	Х	Х
	Apnoea-hypopnea index (AHI) At diagnosis of OSA At follow-up visits (with or without CPAP) ⁸	х	х	х	х	х	x	х	х
	Epworth Sleepiness Scale (ESS)	X	X	Х	Х	Х	Х	Х	Х
	CPAP or alternative (e.g., MAD) and adherence ⁹	Х	х	х	х	х	х	х	X
	Maintenance of wakefulness test (MWT) or Multiple Sleep Latency Test (MSLT)	X		х	х	X	х	х	X
	Beck Depression Inventory	Х		Х	Х	Х	Х	Х	Х
	Fatigue Severity scale	X		Х	Х	Х	Х	X	Х
	Assessment of perceived sleepiness at driving	X		х	х	х	х	х	X
OZAWADE* use	Prescription (when applicable)	X							
	Adherence with the Morisky Medication Adherence Scale 8-item (MMAS-8)		х	х	х	х	х	x	х

- 1. Data collected in the CRF will correspond to data collected in routine practice in the investigating centers.
- Height at inclusion visit only.
- 3. Smoking status: in pack-year.
- 4. Adverse events of special interest include the following cardiovascular events: acute myocardial infarction, new onset of angina, unstable angina, stroke (ischemic, haemorrhagic), transient ischemic attack, new onset atrial fibrillation, unscheduled interventional cardiology procedure (stenting, CABG), new onset hypertension (with new hypertension treatment or a posology adjustment of hypertension treatment), new onset or worsening of peripheral vascular disease or unscheduled intervention, stent thrombosis, heart failure, QT prolongation and cardiovascular death.
- 5. ECG when available.
- 6. Last test available at the time of the visit.
- 7. Duration of sleep.

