9.7.8. Other assessments

Abdominal perimeter, weight and biological assessments will be described at each collection time (except at the 6-month follow-up visit for the biological assessments) by treatment group (OZAWADE® vs. non-OZAWADE®) and overall. Changes from inclusion may be calculated if relevant.

Car/traffic occurrence will also be assessed by a dedicated questionnaire and described.

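### The under-12-month look-back for laboratory values also applies at follow-up, so early or closely spaced visits can carry a pre-inclusion or already reported sample as the follow-up value

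*Protocol*

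**What the plan says.** Section 9.3.9 sets one age limit for the laboratory values: "Biological assessments of less than 12 months (cholesterol, glycemia and triglyceridemia) will be collected at study inclusion and at each follow-up visit", with the 6-month visit excepted. Table 2 repeats it in a single row ("Biological assessment of less than 12 months (cholesterol, glycemia and triglycedemia") that covers inclusion and all annual visits.

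Table 2 gives the annual visit windows as "12M [9-18M[24M [18-30M[36M [30-42M[48M [42-54M[60M [54-66M", each open at its right end. Section 9.2.2.3 gives the nominal times: "The data will be collected during the normal course of patient care at approximately 6, 12, 24, 36, 48 and 60 months".

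No fresh sample is required. Under section 9.3, "only the available measures and assessments will be collected in the CRF".

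On treatment start, section 9.3.7.1 says: "Exposure to OZAWADE® will be collected at inclusion and at follow-up visits (if not started at inclusion"), and it names the prescription date and prescribed dose as the items recorded. OZAWADE can thus begin after inclusion.

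On use of the values, section 9.7.8 states that "biological assessments will be described at each collection time", by treatment group and overall, and adds: "Changes from inclusion may be calculated if relevant".

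**The concern.** A look-back suits a baseline value, where any reasonably recent result before inclusion will do. A follow-up value has to reflect the period since inclusion or since the last visit. Using the same limit for both works only if visits are at least 12 months apart, and the windows in Table 2 do not ensure that. Nothing in the protocol requires a follow-up sample to be later than inclusion or later than the last sample reported.

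At stake is what the laboratory tables in section 9.7.8 mean. A sample entered twice yields a change from inclusion, or from the previous visit, of exactly zero that nobody measured. A pre-inclusion sample entered at Year 1 is tabulated as a follow-up result. Section 9.7.5 counts cholesterol and diabetes among the cardiovascular risk factors, so a reader of this safety study may look at these tables.

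**Working it through.** The protocol states no figure for this point, so there is none to reproduce. The check is one of timing, in months from inclusion.

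**Inputs**
- Permitted sample age: strictly under 12 months (section 9.3.9, Table 2).
- Windows: Year 1 from 9 to <18, Year 2 from 18 to <30, Year 3 from 30 to <42, Year 4 from 42 to <54, Year 5 from 54 to <66 (Table 2).
- Nominal laboratory visits: 12, 24, 36, 48, 60 (section 9.2.2.3; no laboratory collection at 6).

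**1. Earliest admissible sample.** For a visit at month v, the sample must be later than v − 12.
- v = 9: later than 9 − 12 = −3, so up to 3 months before inclusion.
- v = 12: later than 0. Because the limit is strict, only post-inclusion samples qualify.
- v = 18 (window close): later than 6.

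Pre-inclusion samples are therefore admissible only at Year 1 visits from month 9 to before month 12. That is (12 − 9)/(18 − 9) = 3/9 = 33% of the window's length.

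**2. Gap between consecutive annual visits.**
- Minimum: each window opens where the previous one closes (18 − 18, 30 − 30, and so on), so just above 0.
- Nominal: 12.
- Maximum: just under 30 − 9 = 21 for Years 1–2, and just under 24 for later pairs (e.g. 42 − 18).

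If visits fell uniformly and independently in their windows (for illustration only), the gap would be under 12 months in (13.5 + 12 − 18)/12 = 62.5% of Year 1–2 pairs and (24 + 12 − 30)/12 = 50% of later pairs. Here 13.5 and 24 are the midpoints of the earlier windows.

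**3. Condition for the same sample to serve twice.** A gap under 12 months is necessary but not sufficient. If the sample had age a at the earlier visit and the gap is g, re-use requires a + g < 12.
- Visits at months 17 and 24: g = 7, so a < 5.
- Inclusion and a Year 1 visit at month 9: a < 3.
- Inclusion and a Year 1 visit at month 11: a < 1.
- Exact 12-month spacing: a < 0, which is impossible.

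**4. Illustrative share for the inclusion sample at Year 1.** Assume Year 1 visits uniform over 9–18 and inclusion-sample age uniform over 0–12. For a visit at v between 9 and 12, the inclusion sample still qualifies with probability (12 − v)/12. Then:

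(1/9) × ∫ from 9 to 12 of (12 − v)/12 dv = (1/9) × (1/12) × (3²/2) = 4.5/108 ≈ 4.2%.

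This also supposes that no newer result is on file; any newer result lowers it. It concerns Year 1 only. For later pairs, the age condition likewise brings re-use below the percentages in step 2, but the documents give no basis for saying by how much.

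**5. Late starters.** A patient prescribed OZAWADE at month 8, with a sample at month 4 and a visit at month 12, has an admissible sample 8 months old that predates treatment (made-up dates). This can occur at nominal spacing, whenever treatment began less than 12 months before the visit.

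**The case against.** The strongest reply is that the look-back was matched to the annual schedule. With a strict limit and visits at 12, 24, 36, 48 and 60 months, every accepted sample is later than the previous visit. That stands: the overlap needs an early visit or compressed spacing. A second reply is that a sampling-date field, an edit check and rules for attributing values to visits are ordinary content of the CRF, data management plan or SAP. Section 9.6 refers to an annotated CRF and checking procedures, so silence in the protocol does not show that these are absent. That also stands for the date field. It does not dispose of the point, because which sample a site may enter is a rule the protocol itself states, and as stated it admits the wrong ones.

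A reader might also infer more than the documents support:
- *That a third or more of Year 1 values are stale.* The 33% is the part of the window in which a pre-inclusion sample is permitted. It is not a rate of use.
- *That any gap under 12 months means re-use.* The sample's age at the earlier visit counts too (step 3).
- *That mean changes shrink by a known factor.* No re-use rate is given or derivable, so no attenuation can be stated.
- *That the group comparison is biased toward no difference.* A re-used baseline sets that patient's change to zero. If re-use differed between groups, a time trend shared by both would be diluted unequally, which could create a difference. The direction is not known, and nothing shows that one group is tested more often.
- *That the main results are affected.* The primary Poisson model uses risk factors reported at baseline. The values are not a primary, secondary or exploratory endpoint. The time-varying covariates in the secondary Cox model are not named, so no claim can be made there.

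**Conclusion.** The point holds as a minor defect in a stated collection rule. One age limit serves both baseline and follow-up, and the protocol's own windows let a pre-inclusion or previously reported sample pass as a follow-up value when a visit is early or two visits are less than 12 months apart. That follows from the protocol's figures without any assumption.

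The frequency is unknown. The figure of about 4% for re-use of the inclusion sample at Year 1 rests on uniform visit times, uniform sample ages and no newer test, and serves only as an order of magnitude. The consequence is limited to the by-group laboratory descriptions and the optional changes from inclusion in section 9.7.8.

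**What to change.** In section 9.3.9 and the Table 2 row, keep the under-12-month look-back for inclusion only. At follow-up visits accept, in both groups alike, only a sample dated after inclusion and after the last sample reported; otherwise enter 'not available'. Record the sampling date, if the eCRF does not already hold it, with an automatic check against the last reported date.

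Do not make acceptance depend on first intake of OZAWADE: section 9.3.7.1 names the prescription date, not an intake date. With the sampling date recorded, values in patients who start later can be placed before or after the recorded prescription date at analysis.

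The cost is one sentence, one field if missing, and one edit check. No test is added, so the study remains non-interventional. The drawback is that some more follow-up values will be recorded as missing, but they will be visibly missing and not old results shown as current.
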